**Case 1:**

Zero dose adjustments were prescribed to start during the period between last date study drug was dispensed which was Visit(k-1), and the date of the current visit, which is Visit(k).

Compliance (%) =

100 times (# pills dispensed at Visit(k-1) – # pills returned at Visit(k))

*divided by*

([# pills prescribed to be taken on the day of Visit(k-1)] + {[date of Visit(k) – 1 day – date of Visit(k-1)] times [# pills prescribed to be taken per day on 1 day after date of Visit(k-1) thru the day before Visit(k)]})},

where if day of Visit(k-1) is day of Randomization,

then [# pills prescribed to be taken on the day of Visit(k-1)] = 0

**Case 2:**

Only one dose adjustment was made during the period between last date study drug dispensed which was Visit(k-1) and the date of the current visit at which study drug was returned, which is Visit(k).

Compliance (%) =

100 times (# pills dispensed at Visit(k-1) – # pills returned at Visit(k))

*divided by*

([date new dose was prescribed to start – date of Visit(k-1)] times [# pills prescribed to be taken per day starting on date of Visit(k-1) thru the day before the new dose was prescribed to start],

*plus*

[date of Visit(k) – date the new dose was prescribed to start] times [total # pills prescribed to be taken per day starting on date the new dose was prescribed to start thru the day before the Visit(k)])

where if date of Visit(k-1) is date of Randomization,

then let date of Visit(k-1) = {1 + date of Visit(k-1)}

---

Document: \\quintiles.net\enterprise\apps\sasdata\sasb\sas\Keryx\KRX-0502\Biostatistics\Documentation\SAP\

**Case 3:**

A total of  $m > 1$  dose adjustments were made during the period between last date study drug was dispensed which was Visit(k-1), and the date of the current visit at which study drug was returned, which is Visit(k),

Compliance (%) =

100 times (# pills dispensed at Visit(k-1) – # pills returned at Visit(k))

*divided by*

([prescribed start date at dose level for dose adjustment #1 – date of Visit(k-1)] times [# pills prescribed to be taken per day starting on date of Visit(k-1) thru the day dose adjustment #1 was prescribed to start]

*plus*

[the sum over i for i = 1 to (m - 1) of {date new dose # (i+1) was prescribed to start – date new dose # i was prescribed to start} times [# pills prescribed to be taken per day starting on date that new dose # i was prescribed to start thru the day before the new dose # (i+1) was prescribed to start}]

*plus*

[date of day before Visit(k) – date new dose # m was prescribed to start] times [total # pills prescribed to be taken per day starting on date the new dose # m was prescribed to start thru the day before the Visit(k)],

where if date of Visit(k-1) is date of Randomization,

then let date of Visit(k-1) = {1 + date of Visit(k-1)}

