### 6.3.5. Per Protocol Analysis Set

The Per Protocol (PP) Analysis Set will include all subjects in the FAS who have no major protocol deviations that affect the validity of the efficacy measurements (see section 7.2) and have not received additional treatment that affect the validity of the efficacy measurements.

The following criteria exclude a subject from the PP Analysis Set:

- Receive red blood cell transfusions within 4 weeks prior to screening or at any time during the study.
- Receive ESAs (permitted or non-permitted) within 4 weeks prior to screening or at any time during the study.
- Receive IV Iron within 4 weeks prior to screening or at any time during the study.
- Pregnancy during screening or at any time during the study.
- Overall drug compliance < 50% i.e., from randomization to the Week 48 Visit date or to Early Termination date (whichever is earlier). (See section 7.4.1 Compliance Calculation)
- Major violations of eligibility criteria as determined by review prior to database lock.

The PP analysis set will be used for the 24-Week and Final analyses.

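### Case 3 of the SAP compliance formula leaves out one prescribed day, so compliance is slightly overstated for visit intervals with two or more dose changes

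*SAP*

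**What the plan says.** SAP 9.3.2 defines compliance as tablets taken divided by tablets prescribed, and builds the denominator separately for three situations between Visit(k-1) and Visit(k).

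- **Case 1 (no adjustment).** One day's tablets are added separately ("pills prescribed to be taken on the day of Visit" (k-1)). The remaining days run from the following day ("pills prescribed to be taken per day on 1 day after date of Visit" (k-1)), with a multiplier of Visit(k) minus 1 day minus Visit(k-1).
- **Case 2 (one adjustment).** The starting dose runs "thru the day before the new dose was prescribed to start". The last multiplier is the date of Visit(k) minus "date the new dose was prescribed to start] times [total # pills prescribed to be taken per day".
- **Case 3 (two or more adjustments).** The last multiplier is "date of day before Visit" (k) minus the start date of dose #m. The label on the same term says the tablets are those "prescribed to be taken per day starting on date the new dose # m was prescribed to start thru the day before the Visit" (k). The first term is labelled as running "thru the day dose adjustment #1 was prescribed to start".

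For longer periods, the SAP sums the interval denominators. It describes each as the tablets prescribed from Visit(k-1) up to and including the day before Visit(k). SAP 6.3.5 then excludes a subject from the Per Protocol (PP) set for "Overall drug compliance < 50" per cent, measured from randomization to Week 48 or Early Termination. SAP 9.3 also reports the numbers below and at or above 50%, by starting dose and by dosing sequence.

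**The concern.** The same visit interval should give the same number of prescribed days however often the dose changed within it. In Case 3 it does not. The shortfall sits in the denominator, so it can raise computed compliance but never lower it.

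The figure helps decide who is in the primary analysis. The 24-Week and Final efficacy analyses use the PP set (SAP 8.1). SAP 9.6 drops the Full Analysis Set efficacy analyses that the protocol had planned as sensitivity analyses, except in the permitted ESA rescue subgroup. A subject wrongly kept in the PP set would therefore not be offset by an analysis of all treated subjects. The wording also leaves room for two programmers to produce different denominators, depending on whether they follow the multipliers or the labels.

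**Working it through.** The SAP states no numerical result here, so the check is a day count. Write V0 for the date of Visit(k-1), V1 for the date of Visit(k), and D1, …, Dm for the start dates of the adjusted doses.

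**Days counted, from the multipliers in SAP 9.3.2**

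| Case | Sum of multipliers | Total days |
|---|---|---|
| 1 | 1 + (V1 − 1 − V0) | V1 − V0 |
| 2 | (D1 − V0) + (V1 − D1) | V1 − V0 |
| 3 | (D1 − V0) + (Dm − D1) + (V1 − 1 − Dm) | V1 − V0 − 1 |

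The minus one in Case 1 is offset by the separately added day of Visit(k-1). Case 3 has no such offset. The days from Dm through V1 − 1 inclusive number V1 − Dm, one more than the Case 3 multiplier. When Visit(k-1) is Randomization, all three cases lose one day, so the gap remains.

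**Numerical check.** At 3 tablets/day over 28 days:
- Case 1 and Case 2: 3 × 28 = 84
- Case 3 as written: 3 × 27 = 81
- Case 3 ending at V1: 84

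A day-by-day count over 5,000 random dose histories, with two to four adjustments and intervals of 14, 28 or 56 days, gave a Case 3 shortfall equal to dose #m every time, and zero only when dose #m was zero. With the last term ended at V1 there were no mismatches.

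**The first-term label.** Its multiplier is D1 − V0, the same as in Case 2. The missing word *before* changes no number and does not restore the lost day.

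**Effect on overall compliance.** Suppose a roughly constant dose, D counted days and j Case 3 intervals. Computed compliance is then the correct value times D/(D − j). A subject is wrongly kept in the PP set if correct compliance lies from 50 × (D − j)/D up to, but not including, 50%.

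| D (days) | j | Correct compliance wrongly kept |
|---|---|---|
| 336 | 1 | 49.85% to <50% |
| 336 | 3 | 49.55% to <50% |
| 168 | 1 | 49.70% to <50% |
| 28 | 1 | 48.21% to <50% |
| 14 | 1 | 46.43% to <50% |

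**Two illustrations (the tablet counts are assumptions)**
- Full follow-up, 336 days at 4/day: 1,344 tablets prescribed, and 1,340 as computed with one Case 3 interval. With 671 taken, 671/1344 = 49.93% becomes 671/1340 = 50.07%. Only counts of 670 or 671 cross the line.
- Early termination after 28 counted days at 4/day, with a 7-day interruption and the resumption in the same visit interval: (28 − 7) × 4 = 84 prescribed, and 80 as computed. With 41 taken, 41/84 = 48.8% becomes 41/80 = 51.25%.

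**The case against.** The strongest reply is that the intended span is clear and the consequence is slight. Case 3's own label and the multi-visit definition both run through the day before Visit(k), so a careful programmer might notice the mismatch. That helps only in part, because the multi-visit definition points back to the Case 3 expression for its value.

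Case 3 may also be uncommon. It needs two or more adjustments between consecutive site visits, and unscheduled visits also close an interval. Protocol 7.5 and 7.5.2 call for repeat laboratory tests two weeks after a phosphorus-related change, normally as an unscheduled visit, which would often split the interval. Case 3 can still arise. An interruption and resumption for an adverse event are two adjustments, changes may be made by telephone, and maintenance visits are 8 weeks apart. The missing-count rule in SAP 9.3.2 can also merge intervals. The documents give no frequency.

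Three stronger readings are tempting, and the documents do not support them:
- **That compliance of about 48% in one interval would pass the 50% rule.** Over 28 days at 4, 2 and 4 tablets/day for 7, 14 and 7 days, 84 prescribed tablets become 80, and 48% × 84/80 = 50.4%. The PP rule applies to overall compliance, so this matters only if follow-up was about that short.
- **That subjects with the most dose changes are affected.** A subject with many changes, but at most one per interval, stays in Case 2 and is unaffected.
- **That compliance is always inflated.** It is not if the last adjustment in the interval is to zero tablets.

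**Conclusion.** The formula is wrong as written. Case 3 counts one day fewer than Cases 1 and 2, its own label and the multi-visit definition, and nothing elsewhere in the SAP restores that day. The error equals one day at dose #m for each Case 3 interval.

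Its practical size is small. Over 48 weeks at a constant dose, one Case 3 interval raises compliance by 0.3% in relative terms, or about 0.15 percentage points near the cut-off (50 × 336/335 = 50.15). Early terminators are more exposed because the lost day is a larger share of their follow-up. Few PP assignments would be expected to change. That rests on the constant-dose illustration and on few subjects lying so close to 50%; the documents give neither the distribution of compliance nor the number of Case 3 intervals. The modified Per Protocol set used for the 24-Week snapshot has no compliance criterion and is unaffected (SAP 6.3.6). This is a minor correction that does not call the primary analysis into question.

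**What to change.** In SAP 9.3.2, Case 3, make two edits:
1. In the last term, replace the date of the day before Visit(k) with the date of Visit(k), so that the multiplier is Visit(k) minus the start date of dose #m, as in Case 2.
2. In the first-term label, end the starting dose on the day before adjustment #1 was prescribed to start. This corrects the wording only and has no numerical effect.

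Check that the compliance program uses the corrected term, and do so before database lock, because the result helps fix PP membership. No new data, visits or analyses are needed.

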**Special Case:**

**Missing Value for Number of Pills Returned and/or Number of Pills Dispensed**

- For all three cases, Case 1, Case 2 and Case 3 described above:
  - If (# pills returned at Visit(k)) is a missing value then Number of Pills Used Since Last Visit and Compliance Since Last Visit will be missing.
  - If (# pills dispensed at Visit(k-1)) is a missing value,
    - let (# pills dispensed at Visit(k-1)) = # pills dispensed at Visit(n), where n is the largest site visit number less than k – 1 where (# pills dispensed at Visit(n)) is a non-missing value and

calculate compliance (%) using  $\text{Visit}(k - 1)) = \text{Visit}(n)$ , where n is the largest site visit number less than  $k - 1$  where (# pills dispensed at  $\text{Visit}(n))$  is a non-missing value.

#### Compliance Over Period Spanning More Than Two Consecutive Site Visits:

To calculate compliance for any period X that spans more than the period between two consecutive site visits note that the numerator in the expression,

Compliance (%) =

$$100 * \frac{\text{amount of study drug taken during the specific time period, } X}{\text{amount of study drug prescribed to be taken during the specific time period, } X}$$

is 100 times  $\sum_{k=3}^n$  (# pills dispensed at  $\text{Visit}(k - 1) - \# \text{ pills returned at } \text{Visit}(k))$ , where n - 1 is the number of site visits the subject had during the period X and the denominator is

$\sum_{k=3}^n$  (the number of pills *prescribed to be taken from*  $\text{Visit}(k - 1)$  thru the day before  $\text{Visit}(k))$

where (the number of pills *prescribed to be taken from*  $\text{Visit}(k - 1)$  thru the day before  $\text{Visit}(k)$ )

is the denominator of the expression given above for Case 1, Case 2 or Case 3 depending on the number of dose adjustments between  $\text{Visit}(k - 1)$  and  $\text{Visit}(k)$ .

#### 9.4. Routine Laboratory Data

Tables for three groups of laboratory parameters, hematology, clinical chemistry and urine chemistry will be provided. All laboratory tests will be listed. Laboratory test results for all subjects in the safety analysis set will be summarized using descriptive statistics. For the continuous laboratory parameters descriptive statistics will be displayed for the actual values and for the change in value from baseline to each scheduled post-baseline visit. Tables and listings for the 24-Week Analysis will only display statistics for visits during the Dose Titration period. Tables for the Final Analysis will show those visits during the Dose Maintenance period in addition to the Baseline visit but listings for the Final Analysis will be based on observations over the entire study.

Subject's laboratory results for the following laboratory parameters:

---

Document: \\quintiles.net\enterprise\apps\sasdata\sasb\sas\Keryx\KRX-0502\Biostatistics\Documentation\SAP\

- Ferritin
- TSAT
- Hemoglobin
- Serum Phosphorous

are of special interest. Their values will be classified as low or where relevant one of its sub-categories, normal, or high or where relevant one of its sub-categories given the range of values used to identify clinically meaningful abnormalities in a patient with CKD.

The thresholds for potentially significant abnormalities are based upon Common Terminology Criteria for Adverse Events v4.0 (CTCAE) grades and/or clinically meaningful abnormalities in a CKD stage 3- 4 patient. The thresholds are listed in Table 4 below. Table 4 also includes these categories for impaired liver function, i.e., the categories of total bilirubin, ALT and AST as related to identification of potential Hy's Law cases.

Shift tables, for the laboratory parameters of special interest will be produced showing the number and percentage of subjects with Baseline result in each of the categories, low or where relevant the sub-categories of low, normal and high or where relevant the sub-categories of high, whose result at the post-baseline visit is in each of these categories. The shift tables will be provided by starting dose group and the two treatment groups combined. A by subject listing by visit of the subject's values with their classification relative to potentially significant abnormality for each laboratory parameter of special interest will be provided.

By subject listings for every laboratory parameter collected will be provided. Each value will be identified in the by subject listings as being low, normal or high based on the central laboratory reference ranges. For the Final analysis only, if less than 3 subjects received permitted ESA rescue therapy, comparable by subject listings will be provided for this FAS subgroup.

An additional by subject listing by starting dose will be provided of subjects who have a total serum bilirubin value  $> 2 \times \text{ULN}$ . This listing will include the date of first elevated bilirubin; an indicator for  $\text{ALT} > 3 \times \text{ULN}$  and an indicator for  $\text{AST} > 3 \times \text{ULN}$  along with the baseline identifying characteristic variables that are displayed on all other by subject listings.

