Additionally, a Mixed Model Repeated Measures model will be fitted to the change from Baseline Hgb incorporating all visits at which Hgb is measured for each subject. Baseline Hgb and randomized dose group will be applied as fixed effects, as will time (in weeks) and time-by-dose group interaction. An unstructured within-subject covariance structure will be assumed.

TSAT, ferritin, and serum phosphorus will be analyzed in a manner similar to the primary endpoint stated above. Changes for the WPAI questionnaire, the FACIT Fatigue Scale, and frequency and duration of hospitalizations will be analyzed descriptively.

Efficacy analyses will be repeated, substituting the dosing sequence groups for the randomized dose groups if appropriate, based on the distribution in the 4 dosing sequence groups (3-3, 3-6, 4-4, and 4-6 tablets/day). The dosing sequence groups will be determined based on actual doses received by each subject.

Safety:

All safety analyses will be conducted based on the Safety Analysis Set.

Safety data will include AEs, vital signs, and clinical laboratory measurements. Observed data will be listed by subject and summarized using descriptive statistics overall and by dose group based on the Safety Analysis Set.

AEs will be mapped to preferred term and body system using the Medical Dictionary for Regulatory Activities (MedDRA). AEs that begin after the first administration of study medication or pre-existing conditions that worsen after the first dose of study medication are considered treatment-emergent adverse events (TEAEs). The number and percentage of subjects reporting TEAEs will be summarized overall and for each randomized dose group by MedDRA system organ class and preferred term, then by severity, and by relationship to study treatment. Drug-related AEs will be considered those that are related to study drug based on the Investigator's assessment. The number and percentage of subjects reporting serious AEs and the number and percentage of subjects reporting AEs leading to treatment discontinuation will also be summarized overall and for each dose group by MedDRA system organ class and preferred term.

Vital signs and other clinical and laboratory parameters will be measured at baseline and post-baseline visits. Abnormalities observed in these parameters will be summarized using shift tables for all subjects and by randomized dose group.

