15.8.2. Clinical Laboratory Tests

Clinical and laboratory parameters will be measured at baseline and post-baseline visits. Each continuous laboratory variable will be summarized as changes from Baseline for all subjects and by randomized dose group.

Laboratory data will also be classified as low, normal, or high relative to the parameter's reference range for a population with CKD stage 3 to 5. Laboratory abnormalities for all subjects and for each dose group will also be summarized using shift tables.

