**Table 4: Clinical Laboratory Potentially Clinically Significant Criteria**

Parameter	Threshold (Low Criterion/ High Criterion)	Low Criterion (Subcategories)	High Criterion (Subcategories)
Iron Parameter (unit)			
Ferritin (ng/mL)	Clinical	NA	High 1: > 500 to 1000, High 2: > 1000
Transferrin saturation (%)	Clinical	NA	High 1: > =50 to <70 High 2: > =70
Hematology			
Hemoglobin (g/dL)	CTCAE grade 3 /Clinical	< 8.0	> 13
Chemistry			
Phosphorous (mg/dL)	CTCAE grade 2 /Clinical	Low 1: ≥2.0 to <2.5, Low 2: < 2.0	> 9.0
Liver Function			
Hy's Law (Impaired Liver Function)	CTCAE grade 2 /DILI*	NA	High 1: ALT or AST > 3 x ULN to 5 x ULN High 2: ALT or AST > 5 x ULN
Total serum bilirubin value	DILI*	NA	> 2xULN

\*DILI = Drug Induced Liver Injury

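### SAP 9.4 narrows the laboratory shift tables to four parameters without declaring it, and no table in the SAP text counts subjects in its ALT/AST categories by dose group

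*SAP*

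**What the plan says.** **Protocol.** Section 15.8.2 states "Laboratory data will also be classified as low, normal, or high relative to the parameter's reference range", specified there as the range for a population with CKD stage 3 to 5. It adds "Laboratory abnormalities for all subjects and for each dose group will also be summarized using shift tables". The synopsis makes the same commitment for vital signs and other clinical and laboratory parameters: "Abnormalities observed in these parameters will be summarized using shift tables for all subjects and by randomized dose group". Neither place names a subset of parameters.

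**SAP.** Section 9.4 begins broadly: "Laboratory test results for all subjects in the safety analysis set will be summarized using descriptive statistics", with tables for hematology, clinical chemistry and urine chemistry. It then singles out ferritin, TSAT, hemoglobin and serum phosphorus, and for these alone says "Shift tables, for the laboratory parameters of special interest will be produced". All other parameters are flagged low, normal or high, against central-laboratory ranges, in by-subject listings.

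For the liver, Table 4 sets two bands, "High 1: ALT or AST > 3 x ULN to 5 x ULN" and "High 2: ALT or AST > 5 x ULN", and a bilirubin threshold of more than 2 x ULN. The output that follows is a listing: "An additional by subject listing by starting dose will be provided of subjects who have a total serum bilirubin value" above 2 x ULN, with indicators for ALT and AST above 3 x ULN.

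Section 9.6 sets out the changes from the protocol's analyses. It declares, with a reason, that the vital-sign analyses are dropped. It has no entry for the laboratory shift tables.

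**The concern.** Clinically significant change in laboratory results is a stated safety endpoint (Protocol 6.1.3, SAP 3.2.3), and the study's objective covers the safety of different dose regimens. A shift table answers a by-group question: how many subjects moved from normal to abnormal. Distribution summaries and listings do not answer it directly. If the tables are cut to four parameters, that answer is lost for the rest, and a reader who relies on 9.6 to learn what changed will not know it.

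The liver tests show the problem most clearly, because the SAP defines severity bands for them and then describes no table that uses the bands.

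**Working it through.** The plan states no figure to reproduce on this point. The check is a comparison of texts and a count.

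**1. Scope of the shift tables.** Inputs: the panels in Protocol 13.1.4.1 to 13.1.4.4, the visits in Protocol Table 2, and the special-interest list in SAP 9.4.

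| Panel | Named items | With a shift table in SAP 9.4 |
|---|---|---|
| CBC | 7 | 1 (hemoglobin) |
| Chemistry profile | 17 | 1 (phosphorus) |
| Iron studies | 5 | 2 (TSAT, ferritin) |
| Total | 29 | 4 |

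Items without a shift table: 29 − 4 = 25. Adding iPTH and the two FGF23 assays gives 32 − 4 = 28. These are minimum counts, because WBC differential and RBC indices are each counted as one item.

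**2. Declaration.** The entries in SAP 9.6 cover the safety set definition, ad hoc analyses, the modified per-protocol set, added endpoints and plots, vital signs, the FAS analyses, the baseline-by-visit term, multiple imputation and the interim analysis. The laboratory shift tables are not among them.

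**3. Where a raised ALT or AST would appear in the SAP's outputs.**

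| Case | Shift table | Bilirubin-triggered listing | Elsewhere |
|---|---|---|---|
| ALT/AST >3 to 5 x ULN, bilirubin ≤2 x ULN | No | No | By-visit statistics; value flagged high in the general listing; AE if it qualifies |
| ALT/AST >5 x ULN, bilirubin ≤2 x ULN | No | No | Same as above |
| ALT/AST >3 x ULN, bilirubin >2 x ULN | No | Yes, as above 3 x ULN | Same as above |
| ALT/AST >5 x ULN, bilirubin >2 x ULN | No | Yes, but only as above 3 x ULN | Same as above |

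No row yields a number and percentage of subjects by dose group in the Table 4 bands, and the band above 5 x ULN is not used by any specific output.

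**4. Whether the by-visit maximum fills the gap.** SAP 6.2 includes minimum and maximum in the descriptive statistics, so an extreme value at a scheduled visit can show. It shows as one number, not as a count of subjects. SAP 6.5.4 also keeps only the latest assessment in a window. The Week 24 window is days 156 to 197 with target day 169, so a repeat up to 197 − 169 = 28 days after an on-target visit replaces it. Protocol 7.5 requires repeat testing that guides dosing to include the full chemistry profile, and so ALT and AST. If the rule is applied to the laboratory tables as written, a peak followed by a lower repeat in the same window drops out of the by-visit statistics, maximum included.

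**5. Whether adverse-event reporting fills it.** Protocol 13.2.2 does not require a laboratory change to be reported as an AE unless it is deemed clinically significant, leads to discontinuation or constitutes an SAE. Qualifying post-dose events reach the TEAE tables. That count depends largely on investigator judgement and does not correspond to the Table 4 thresholds.

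**The case against.** The strongest reply is that little is lost. Every parameter has by-visit summaries of value and change, with quartiles, minimum and maximum. Bicarbonate also has a repeated-measures analysis with confidence intervals (SAP 8.3). Clinically significant values must be recorded as AEs and are tabulated by dose group. Listings carry the actual values. The four chosen parameters match the drug's iron and phosphate effects and the dosing rules. SAP 9.4 ties the liver categories to finding potential Hy's Law cases, and the bilirubin-triggered listing serves that purpose.

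Most of this stands. A reader might infer that the other laboratory abnormalities are never summarised, or are reported as means only; the documents contradict both. Nor can one say that a few large rises would leave the summaries unmoved. Suppose ALT has mean 20 and SD 8 U/L with a ULN of 40 (illustrative assumptions), and 4 of 200 subjects reach 200 U/L at one visit. The mean becomes (196 × 20 + 4 × 200)/200 = 23.6, the SD rises to about 26, and the maximum reads 200.

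A reader might also infer a known liver signal from the exclusion of subjects with transaminases above 3 x ULN. That is an eligibility limit. Protocol 7.5.2 has no liver-specific dosing guidance, and Protocol 5.2 names gastrointestinal events as the most frequent.

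What the reply does not supply is the by-group count of subjects with abnormal values that the protocol promised, or any entry in 9.6 explaining its removal.

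**Conclusion.** The point holds as a reporting gap and an undeclared change. Shift tables go from laboratory parameters in general to 4 of at least 29 routine items, leaving 25 without by-group abnormality counts in the SAP text, and SAP 9.6 is silent. The ALT/AST band above 5 x ULN has no specific output, and transaminase rises above 3 x ULN without bilirubin above 2 x ULN have no liver-specific output.

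It does not show that laboratory safety goes unreported or that a liver problem is suspected, and it leaves the primary endpoint untouched. The conclusion rests on the SAP text alone: the table shells named in SAP 11.5 are a separate document that was not available. The correction is still worth making, because it restores part of a protocol-specified safety analysis from data already collected.

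**What to change.** 1. In SAP 9.4, add a table by starting-dose group and combined, on the Safety Analysis Set. It should give the number and percentage of subjects whose worst post-baseline value, from scheduled or unscheduled draws, falls in each Table 4 category for ALT, AST and bilirubin. Include the joint criterion of ALT or AST above 3 x ULN with bilirubin above 2 x ULN, and state whether both must come from the same draw. Using the worst value is a recommendation here, not a protocol requirement; it avoids the loss caused by the last-in-window rule.
2. For the remaining parameters, either produce the protocol's shift tables with its stated reference range (CKD stage 3 to 5), or declare and justify the narrowing in SAP 9.6. Using central-laboratory ranges for these tables would be a further departure and would itself need declaring.

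**Cost.** Some table programming and a longer output package; no new data. The central-laboratory flags planned for the listings do not provide the protocol's CKD-range classification, so full shift tables take more work than the liver table. Declaring the narrowing takes one entry in 9.6.
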